The primary study outcome is to determine the feasibility of enrolling and randomizing AIS patients to a therapeutic intervention within less than one hour of ED presentation. Secondary outcomes of potential therapeutic effect to inform future clinical trial(s) include penumbral salvage at repeat imaging, change in NIHSS over the first 24 hours, and 3-month mRS. To assess potential adverse effects on markers of worsening stroke severity and possible hyperoxic lung injury, levels of MMP-9, IL-6, and IL-8 will be measured at initiation, 4 hours and 24 hours. Further analysis of additional biomarkers will be considered in the future.

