7. STUDY PROCEDURES

As part of the screening and enrollment process, patients with suspected AIS will have either a non-contrast CT head with RAPID calculation of ASPECT score or a CT-perfusion head. Using standard stroke alert treatment protocols at this institution, the RAPID software is used in most potential stroke patients at our institution and will be used to calculate infarct and penumbral volume and targeted diffusion/perfusion mismatch for this study. As part of the screening process, medical charts and EMS reports will be accessed by study personnel as needed to ensure potential subjects meet all inclusion/exclusion criteria. The screening and enrollment procedures along with collection of initial vitals will occur almost simultaneously given the very acute nature of the presentation and desired short interval from ED presentation to randomization. No data will be collected during the screening process that is not part of routine patient care prior to subject enrollment. Routine patient demographics, past medical history, medications, and prehospital assessments will be obtained from chart review. No research data that is not already part of routine patient care will be entered into the subject medical records. Randomization will occur in a 1:1 fashion between the two treatment groups. The estimated study duration is 30 months to allow for full enrollment of subjects and the 3-month mRS assessment. Each subject will be followed for a total of 90 days from enrollment to final assessment. No results from this study will be shared with subjects.

[figure not shown]
Once consented and enrolled in the study, subjects will have the following procedures: (See Table 1 for Schedule of Activities).

1. *Infarct progression:*

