- a. Initial CT-perfusion head or non-contrast CT-Head with RAPID ASPECT score – multimodal CT-head imaging will be obtained upon ED presentation according to local stroke protocols. Targeted mismatch criteria will be based on previous standards identified in the DEFUSE 3 trial, using RAPID generated CT maps (RAPID, iSchema View, Menlo Park, CA)⁵⁷. This study measurement will be completed as part of the screening process to ensure eligibility with regards to a target mismatch lesion. However, upon completion of the CT-perfusion or non-contrast CT-Head, the total volume of at-risk tissue (both penumbral and infarcted tissue) will also be determined and recorded. This is part of the routine medical treatment for acute stroke patients.
- b. Follow-up MRI-head, or a repeat CT-head in patients unable to obtain an MRI, will be obtained at roughly T3 according to standard stroke imaging protocols. The total volume of infarcted tissue will be determined and recorded. Repeat

imaging usually between 24-72 hours is part of the standard of care for most stroke patients to ensure there has not been hemorrhagic conversion. Only these repeat imaging studies that were routinely obtained for standard patient care will be used for further determination of infarct progression. Specific study-dedicated imaging will not be obtained.

- c. The ratio of the volume of at-risk tissue (T0 – penumbral and infarcted tissue) to the volume of final infarct at subsequent reimaging will be compared between the placebo and hyperoxia groups. Volume assessments will be generated from both the CT-perfusion or non-contrast CT-Head at screening and the subsequent MRI using RAPID (iSchema View). These image files contain PHI, but are de-identified prior to processing by RAPID under the below process and PHI remains within the UCHealth firewall.

2. Analysis of serum markers of free radical ischemic-reperfusion injury and hyperoxic lung injury:

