17. DATA ANALYSIS PLAN

The primary endpoint of this study is feasibility. We hypothesize that the challenges of enrolling and randomizing AIS patients to a therapeutic intervention within less than one hour of ED presentation can be addressed. The number of potential subjects meeting the inclusion criteria and the relative rates of enrollment over time will be tracked. Additionally, the timing to enrollment and initiation of treatment intervention will be monitored. The primary endpoint of this study is feasibility as measured by the mean time from presentation to the ED to randomization and initiation of intervention. We hypothesize that we will be able to enroll, randomize and initiate treatment intervention in less than one hour for 80% of the enrolled subjects.

This study is not powered to detect significant differences in secondary or exploratory outcomes. However, analysis of secondary outcomes will occur both on an intention-to-treat and a per-protocol basis. Penumbral salvage will be reported as an average and as a standard deviation of the mean. We plan to enroll a total of 200 patients. Based on previous data that showed a decrease in the relative infarct volume growth (infarct volume at presentation/infarct volume at 4 hours) in patients treated with hyperoxia (87.8 +/-22%) compared to controls (149.1 +/- 41%)²⁹, 5 patients per arm would be needed to detect a similar difference with a power of 90% and type I error rate (α) of 0.05⁶². However, this effect was seen in a small study with less than 10 patients per treatment arm. Thus, such dramatic changes in infarct volume may not be expected, but even a smaller reduction in infarct volume will be clinically important as small reductions in infarct volume can have profound clinical effects if it is in a key cerebral territory. If you assume 20% of patients for some reason do not receive standard follow-up imaging to allow for calculation of infarct progression, a standard deviation of 41%, 80% power and α of 0.05, the proposed sample size will be able to detect an absolute difference in infarct volume growth of 18% between the control and hyperoxia.

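### The Section 7 imaging ratio has no value when the final infarct is zero; its link to penumbral salvage, its scan time and its detectable difference also need settling

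*Combined protocol and SAP*

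**What the plan says.** Section 7, under infarct progression, item (c), compares between arms "The ratio of the volume of at-risk tissue (T0 – penumbral and infarcted tissue) to the volume of final infarct at subsequent reimaging". It gives no rule for a final infarct of zero.

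Section 4 lists secondary outcomes that "include penumbral salvage at repeat imaging". Section 17 adds that "Penumbral salvage will be reported as an average and as a standard deviation of the mean". Neither gives a formula or refers to the Section 7 ratio.

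On timing, Section 7 item (b) states: "Follow-up MRI-head, or a repeat CT-head in patients unable to obtain an MRI, will be obtained at roughly T3". Table 1 defines T3 as 3 months +/- 2 weeks after T0, but marks the repeat scan under T2, which is 24 +/- 4 hours. Item (b) also says that repeat "imaging usually between 24-72 hours is part of the standard of care for most stroke patients", and that only routine scans will be used.

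Section 17 cites relative infarct growth of 87.8 +/- 22% with hyperoxia and 149.1 +/- 41% in controls. It calls this a decrease with hyperoxia, and prints the measure as volume at presentation divided by volume at 4 hours. From an SD of 41%, 20% without follow-up imaging, 80% power and alpha 0.05, it derives a detectable difference in infarct growth of 18%. It also says that the study is not powered for secondary outcomes.

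**The concern.** The ratio is oriented so that treatment success drives the denominator towards zero. A patient whose at-risk tissue is entirely spared cannot be scored, and one who is almost entirely spared gets an extreme score. Such patients are plausible. Entry needs only findings suggestive of infarction, with a mismatch profile or an ASPECT score of 10 (Section 4.2), and Section 13 foresees that some enrolled patients may turn out to have a diagnosis other than stroke.

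The surrounding text does not settle what is analysed. The named outcome has no formula, the text and the schedule differ on when the scan takes place, and the only precision figure belongs to another quantity at another time. Analysts would have to choose the formula, the eligible scans and the handling of zeros after the data are in. Section 4 says that these outcomes are meant to inform a future trial.

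**Working it through.** **The plan's own figure.** Inputs from Section 17: 200 patients, 1:1, 20% without follow-up imaging, SD 41, 80% power, alpha 0.05 (taken as two-sided; the plan does not say).
- Evaluable per arm: 100 x 0.8 = 80.
- Detectable difference: (1.960 + 0.842) x 41 x sqrt(2/80) = 18.2 points. The stated 18% reproduces.
- The SD of 41 comes from growth between presentation and 4 hours. Table 1 has no scan at 4 hours. No SD is given for the Section 7 ratio, so 18% is not its precision.

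**Direction of the growth fraction.** Taken as printed (presentation / 4 hours), the 4-hour volume relative to presentation is:
- Controls: 1/1.491 = 0.67, so infarcts shrink to 67%.
- Hyperoxia: 1/0.878 = 1.14, so infarcts grow to 114%.

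This is the opposite of the sentence. Read as 4 hours / presentation, controls grow by 49.1% and hyperoxia infarcts shrink by 12.2%, as the sentence intends. The difference (61.3 points) and the SDs are the same either way, so no sample-size figure changes.

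**Behaviour of the ratio.** All volumes and zero counts below are illustrative; the documents give none. With 50 mL at risk:

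| Final infarct (mL) | At-risk / final | Final / at-risk |
|---|---|---|
| 50 | 1 | 1 |
| 5 | 10 | 0.10 |
| 1 | 50 | 0.02 |
| 0.5 | 100 | 0.01 |
| 0 | undefined | 0 |

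*Zero infarcts.* Take 80 per arm, each with 50 mL at risk and 25 mL final, except 8 zero infarcts in control and 16 in hyperoxia.
- Plan's ratio: 50/25 = 2.00 in the 72 and 64 patients who can be scored, so there is no difference.
- Final / at-risk, all 80 scored: 72 x 0.5/80 = 0.45 and 64 x 0.5/80 = 0.40.
- The median of final / at-risk is 0.50 in both arms, and the rank-sum p is 0.078. Only the count of zeros, 8 against 16, shows the difference plainly.

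*One near-zero infarct.* Take 79 such patients plus one with 1 mL final.
- Plan's ratio: (79 x 2 + 50)/80 = 2.60 instead of 2.00; the SD goes from 0 to 5.4.
- Final / at-risk: (79 x 0.5 + 0.02)/80 = 0.494 instead of 0.500.

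*The mirror case.* Take 79 such patients plus one with 1 mL at risk and 25 mL final.
- Final / at-risk: (79 x 0.5 + 25)/80 = 0.806, SD 2.7; the median stays at 0.50.
- Turning the ratio round therefore does not make a mean safe. Sections 4.1 and 4.2 set a mismatch ratio above 1.2 but no minimum volume.

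**Scan times.** T2 runs from 20 to 28 hours and T3 is about 3 months, so the two cannot both hold. The 24-72 hour range overlaps T2 from 24 to 28 hours.

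**The case against.** Several objections have force, and they limit the point.

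- *The mean and SD are planned for penumbral salvage, not for the Section 7 ratio.* This is correct. The statement about the mean holds only if the two are the same outcome, which no passage says. The undefined value at zero infarct does not depend on that link.
- *Section 2 cites salvage of about 70% in controls and 120% with hyperoxia.* A measure that is better when higher and can exceed 100% would fit a ratio oriented as in Section 7. Section 2 gives no formula, so this does not settle the definition, but turning the ratio round does cost comparability with those figures.
- *The vanishing benefit is built into the example.* It is: the zero counts were chosen to show the mechanism. A reader might infer that a real effect would be lost in this trial; the documents give no rate of zero infarcts and do not support that.
- *Three scan times in conflict?* A reader might infer this. The 24-72 hour range describes usual care and partly overlaps T2. The contradiction is between T3 and T2, and T3 may be a labelling slip.
- *No baseline volume for patients entered on non-contrast CT?* This too might be inferred, since the only RAPID output described for that scan is the ASPECT score. But Section 7 says "Volume assessments will be generated from both the CT-perfusion or non-contrast CT-Head at screening and the subsequent MRI using RAPID", and it describes the initial imaging as multimodal. How many patients will lack a baseline volume is unknown.

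**Conclusion.** The concern holds in a limited form. The Section 7 ratio is undefined for the best outcome and unstable near it, and no rule is given. How often this will occur cannot be determined from the documents. The conflict between T3 and T2 and the inverted growth fraction are shown by the documents' own text and figures.

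A reader might infer that the 18% or the sample size is wrong. It is not: the arithmetic reproduces, the inversion leaves it unchanged, and Section 17 labels the 18% as infarct growth. It simply does not describe the trial's own imaging outcome. The primary feasibility endpoint is untouched, and the plan disclaims power for secondary outcomes. This should be fixed, but it does not threaten the trial's main purpose.

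**What to change.** In Sections 7 and 17 and Table 1:

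1. State that penumbral salvage is the Section 7 imaging outcome, and define it as final infarct volume / at-risk volume. Zero infarct then takes the best value, 0. Keep values above 1 as they are, and do not describe 1 minus the ratio as a share, since it can be negative.
2. Compare the arms with a rank-based test that allows ties. Report median and IQR, together with the number with zero final infarct by arm, because the median alone can hide that difference.
3. Report final infarct volume by arm for all patients with follow-up imaging, including those whose baseline at-risk volume is missing or zero. Count those patients by arm.
4. Correct the growth fraction in Section 17 to 4 hours / presentation. State that the 18% applies to 4-hour growth and that no detectable difference is available for the trial's own imaging outcome. Do not replace it with a rank-scale figure that assumes no ties and 80 evaluable per arm.
5. Reconcile the T3 and T2 passages and record the actual scan time.

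This is a change of wording, with no new scans or patients. The costs are that the plan loses a stated detectable difference for this outcome, the ratio analysis may cover fewer than 80 per arm, and the values will not be directly comparable with the salvage percentages cited in Section 2.

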5. *Vital signs* - The determination of need for additional supplemental oxygen in a patient that becomes hypoxic (pulse oximetry<94%) will be determined by the subject's treating physician irrespective of study interventions. Should a patient be found to require additional supplemental oxygen while enrolled in the study, this will be noted and the patient will continue through the final study assessments. The patient's treating physician will also be responsible for routine monitoring and interpretation of other vital signs such as blood pressure and heart rate. If at study assessment time points the study personnel note a subject to have significant vital sign abnormalities (SpO₂<94%, SBP>180mmHg, DBP>110mmHg, SBP<90mmHg, HR>120, HR<50), the study PI and patient's treating physician will be notified to ensure proper documentation. Interventions will be left to the discretion of the patient's treating physician.

Table 1: Schedule of Activities:

Procedures	Baseline/Enrollment ED presentation -T0 (ED arrival +/-60min)	T1 (T0+4hours +/- 20min)	T2 (T0+24hours +/- 4hours)	T3 - Final Assessment (T0+3mo +/- 2weeks)
Informed consent	X			
Demographics	X			
Medical history	X			
Randomization	X			
Administer study intervention		X		
Vital signs: HR, BP, RR, SpO ₂	X	X	X	
ABG		X		
CT-perfusion or CT-head with ASPECTS	X			
Repeat MRI-head (CT-head if unable to get MRI) ^a			X	
Serum sample ^b	X	X	X	
NIHSS	X	X	X	
mRS	X			X
Adverse event review and evaluation		X	X	

^a only routine re-imaging will be obtained
^b tested for selected biomarkers (IL-6, IL-8, and MMP-9)

Assessment of study intervention adherence:

1. Compliance with study interventions will be directly observed at the given time points. If at any observation period a subject is found not to be compliant with the study intervention, medical records will be reviewed to determine the timing of termination of the supplemental oxygen/medical air.
2. All cases of non-compliance with study interventions will be recorded.

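### The one-hour feasibility measures count only enrolled subjects, so eligible patients missed through delay never count against feasibility

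*Combined protocol and SAP*

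**What the plan says.** Section 4 (Study Design) sets the primary outcome as whether patients with acute ischemic stroke can be enrolled and randomized inside an hour of reaching the ED. Section 17 (Data Analysis Plan) turns this into two measures:

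- a mean: "feasibility as measured by the mean time from presentation to the ED to randomization and initiation of intervention";
- a proportion: "We hypothesize that we will be able to enroll, randomize and initiate treatment intervention in less than one hour for 80% of the enrolled subjects".

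On accrual, Section 17 adds: "The number of potential subjects meeting the inclusion criteria and the relative rates of enrollment over time will be tracked". It attaches no threshold to these counts and no commitment to report them as part of the primary result. The target of 200 is in Section 4.1. Section 7 gives the time frame: "The estimated study duration is 30 months to allow for full enrollment of subjects", plus the 3-month assessment.

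Table 1 in Section 7 marks consent and randomization in the T0 column, with the window "ED arrival +/-60min". The row "Administer study intervention" is marked under T1, not in that column. The eligibility list in Section 4.2 contains no limit on the time from ED arrival to randomization; its only clock is last known well within 12 hours, under criterion 4b. Section 6 describes the one-hour interval as a goal. Section 16 provides for monthly review of the screening and enrollment logs.

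**The concern.** The question in Section 4 is about patients who present. Both measures in Section 17 are about patients who were enrolled. An eligible patient who is not enrolled because the process took too long contributes no time to the mean and does not enter the denominator of the proportion. The protocol itself points to sources of delay: the capacity form takes 5 to 10 minutes and the legally authorized representative may not be in the ED (Section 6), and RAPID imaging must be available before eligibility is known (Sections 4.2 and 7). Patients lost this way are the ones most informative about infeasibility, so leaving them out tilts the result towards success.

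A proportion among enrolled subjects also says nothing about how many were enrolled. The Table 1 window adds an ambiguity. One site could stop randomizing at 60 minutes while the other continues and records late subjects as misses, and their rates would then not be comparable. Section 2 says the project is meant to inform the design of a later trial, and that trial would need the yield per eligible patient.

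**Working it through.** **The plan's own figure.** The 80% comes with no null rate, power or precision target, so there is no derivation to reproduce. At the planned size it means 0.80 × 200 = 160 subjects on time.

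**1. Dependence on sample size.** The criterion is x/N ≥ 0.80, with x the number on time. Exact (Clopper-Pearson) 95% intervals at the smallest passing count:

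| Enrolled N | Passing count x | x/N | Exact 95% CI |
|---|---|---|---|
| 200 | 160 | 80% | 73.8% to 85.3% |
| 100 | 80 | 80% | 70.8% to 87.3% |
| 50 | 40 | 80% | 66.3% to 90.0% |
| 20 | 16 | 80% | 56.3% to 94.3% |

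The point estimate reads the same in every row; only the precision changes.

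**2. The same result per eligible patient.** Let E be the number of screened-eligible patients. The smallest share of eligible patients treated within the hour that still gives 80% among enrolled is 0.80 × N/E. The documents do not give E; 250 to 1000 is an assumed range.

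| E (assumed) | N = 200 | N = 20 |
|---|---|---|
| 250 | 160/250 = 64% | 16/250 = 6.4% |
| 400 | 160/400 = 40% | 16/400 = 4.0% |
| 1000 | 160/1000 = 16% | 16/1000 = 1.6% |

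All six cells meet the stated 80%.

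**3. What the Table 1 window does.**

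- *Read as a limit on randomization.* Every on-protocol subject is randomized within 60 minutes at any N (apart from the boundary at exactly 60), and the mean time to randomization cannot exceed 60 minutes. The randomization component then carries no information. Treatment initiation is not covered by that column and can still be late.
- *Read as a schedule target.* Late subjects can be enrolled and count as misses. With X ~ Binomial(200, 1 − late share), P(X ≥ 160) is:

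| True late share | P(at least 160 of 200 on time) |
|---|---|
| 15% | 0.978 |
| 20% | 0.542 |
| 25% | 0.058 |
| 30% | 0.001 |

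The same probabilities apply if randomization is capped and lateness arises only at treatment initiation. So the criterion can fail under either reading.

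**4. Implied accrual.** If recruitment fills the 30 months less 3 months of follow-up, 200/(30 − 3) = 200/27 = 7.4 per month. This rate is inferred; the protocol does not state it.

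**The case against.** The strongest reply is that the plan already looks beyond enrolled subjects. The paragraph that defines the primary endpoint tracks eligible patients and enrollment rates, and the logs are reviewed monthly. The 80% is worded as a hypothesis, the mean has no cutoff, and there is no formal pass/fail rule. This stands in part: the inputs are planned, and it would be wrong to say that the plan would formally declare success on failed accrual. What is missing is a commitment to report those counts within the primary result. Without it, the only number offered as a benchmark is conditional on enrollment.

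A reader might also infer from Table 1 that the 80% is met by construction. The documents do not support that. The ±60 minutes is a heading in a schedule that covers many baseline procedures. Section 4.2 has no such limit, Section 6 calls the hour a goal, and an 80% hypothesis itself presupposes that some enrolled subjects will be late. Even a strict cap would secure randomization only, not initiation.

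Two further inferences should be resisted. The 7.4 per month is not a protocol standard, and making it a success threshold would be a preference rather than a correction. The minus sign in the window has no practical effect, because consent takes place in the ED and time is measured from presentation.

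**Conclusion.** The point holds as a limitation of the primary endpoint. Both stated measures are conditional on enrollment and so cannot by themselves answer the question set in Section 4. An 80% result is compatible with 64% down to 16% of eligible patients treated within the hour at full enrollment, if 250 to 1000 are eligible, and with far less if enrollment is small. The tilt towards success rests on the assumption that some eligible patients go unenrolled because of delay; the documents do not say how many.

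The window matters only conditionally. If a site enforces it, the randomization component becomes automatic. If not, the criterion is a real test: with 25% of subjects late, the chance of reaching 160 of 200 is about 6%. No figure in the protocol is shown to be arithmetically wrong. This is a cheap improvement in what the feasibility result can support.

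**What to change.** - **Table 1.** State that the 60 minutes is a target, and that eligible patients reached later may still be randomized and count as misses. This agrees with Sections 4.2 and 6.
- **Section 17, denominator.** Report, as part of the primary feasibility result, the proportion randomized and started within 60 minutes of ED arrival among all screened-eligible patients from the screening logs. Give it alongside the proportion among enrolled subjects, each with an exact 95% CI.
- **Section 17, accrual.** Report achieved accrual descriptively against the planned 200 in about 30 months. If a monthly rate is quoted, label 7.4 as inferred from 27 months of recruitment and not as a criterion.

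The cost is mainly wording, since eligible numbers are already tracked and the logs already reviewed. The logs would need to show who was eligible but not enrolled. Recording the reason would help separate delay from refusal, because both lower the share among eligible patients. The downside is a less favourable feasibility figure.
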